5.1.2. Enrollment Criteria

Entered patients are eligible for enrollment into the study (eligible for randomization) only if they continue to meet all of the entry criteria above, and meet all of the following enrollment criteria at the time of randomization (Visit 2):

Type of Patient and Disease Characteristics

- [6] Have a positive ANA (HEp-2 ANA titer $\geq 1:80$) and/or a positive anti-dsDNA (≥ 30 IU) as assessed by a central laboratory at screening.

Note: The ANA and/or anti-dsDNA measurement may be repeated once within approximately 2 weeks of the initial value, and the value resulting from repeat testing may be accepted for enrollment eligibility if it meets the eligibility criterion.

- [7] Have a SLEDAI-2K score ≥ 4 based on clinical symptoms (not including lab values) at randomization.
- [8] Have active arthritis and/or active rash as defined by the SLEDAI-2K at randomization.

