9.2.1. General Considerations for Analyses

In general, continuous data will be summarized in terms of the mean, standard deviation, minimum, maximum, median, and number of observations. Categorical data will be summarized as frequency counts and percentages.

Comparisons between the baricitinib 4-mg or baricitinib 2-mg and placebo groups will be performed for all analyses for the Double-Blinded Treatment Period. No adjustment for multiplicity will be done for these comparisons.

Treatment comparisons of categorical efficacy variables will be made using a logistic regression analysis with treatment, baseline disease activity (SLEDAI-2K < 10 versus SLEDAI-2K ≥ 10), baseline anti-dsDNA status (positive; negative), and region in the model. The proportions and 95% confidence interval (CI) will be reported. Missing data will be imputed using the NRI method.

Treatment comparisons of continuous efficacy and health outcome variables will be made using mixed-effects models for repeated measures (MMRM) model with treatment, baseline score,

baseline disease activity (SLEDAI-2K <10 versus SLEDAI-2K ≥ 10), baseline anti-dsDNA status (positive; negative), region, visit, and the interaction of treatment-by-visit as fixed factors. An unstructured covariance matrix will be used to model the within-patient variance-covariance errors. Type III sums of squares for the least squares (LS) means will be used for the statistical comparison; the 95% CI will also be reported. Treatment group comparisons with placebo at Week 24 and other visits will be tested.

Fisher exact test will be used for all AE, baseline, discontinuation, and other categorical safety data. Continuous vital signs and laboratory values will be analyzed by an analysis of covariance (ANCOVA) with treatment and baseline values in the model. Other continuous safety variables will be analyzed based on t-tests, or as otherwise stated.

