9.2.3. Baseline Definition

Baseline will be defined as the last available value before the first dose of investigational product for both efficacy and safety analyses. In most cases, this will be the measure recorded at Week 0 (Visit 2). Change from baseline will be calculated as the visit value of interest minus the baseline value. For the post-treatment Follow-up Period, the baseline is defined as the last nonmissing assessment on or prior to entering the post-treatment Follow-up Period, that is, on or prior to the Week 24 visit (Visit 9), or the end of treatment visit (including ETV).

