9.4.2. Secondary Analyses

Treatment comparison between baricitinib dose regimens (4-mg or 2-mg) and placebo for the change from baseline in SLEDAI-2K score at Week 24, and the change from baseline in patient's global assessment of disease activity at Week 24 will be analyzed using MMRM method with treatment, baseline disease activity (SLEDAI-2K <10 versus SLEDAI-2K \geq 10), baseline anti-dsDNA status (positive; negative), region, visit, and the interaction of treatment-by-visit as fixed factors. An unstructured covariance matrix will be used to model the within-patient variance-covariance errors. Type III sums of squares for the LS means will be used for the statistical comparison; the 95% CI will also be reported. Treatment group comparisons with placebo at Week 24 and other visits will be tested.

Treatment comparison between baricitinib dose regimens (4-mg or 2-mg) and placebo for the proportion of patients achieving a SRI-4 response and for the proportion of patients achieving a reduction of \geq 4 points in SLEDAI-2K score at Week 24 will be analyzed using the logistic regression model with treatment, baseline disease activity (SLEDAI-2K <10 versus SLEDAI-2K \geq 10), baseline anti-dsDNA status (positive; negative), and region in the model. The proportions and 95% CI will be reported. Missing data will be imputed using the NRI method.

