Appendix 2. Schedule of Activities

Schedule of Activities, Protocol I4V-MC-JAHH

	Screening		Double-Blinded Treatment									Follow-Up
Visit Number	V1	V1a ^a	V2 ^b	V3	V4	V5	V6	V7	V8	V9	ET ^{c,d}	V801 ^{d,e}
Study Week	-6		0	2	4	8	12	16	20	24	any	28 or last dose + 4 weeks
Study Day	-42 to -3		1	15 ± 3	29 ± 4	57 ± 4	85 ± 4	113 ± 4	141 ± 4	169 ± 4	any	197 ± 5 or last dose + 28 ± 5 days
Procedure												
Informed consent	X											
Medical history	X											
Physical examination	X											
Symptom-directed physical examination			X	X	X	X	X	X	X	X	X	X
Previous SLE therapy	X		X									
Patient demographics	X											
Height			X									
Weight	X		X	X	X	X	X	X	X	X	X	X
Waist circumference			X				X			X	X	
Vital signs (BP, pulse, temperature)	X		X	X	X	X	X	X	X	X	X	X
Habits ^f	X											
ECG ^g	X											
Inclusion/exclusion criteria review for entry	X											
Inclusion/exclusion criteria review for enrollment			X									
Administer TB test ^h	X											
Read PPD test if used for TB testing		X										
Chest x-ray ⁱ	X											
Preexisting conditions	X		X									
Adverse events			X	X	X	X	X	X	X	X	X	X

	Screening		Double-Blinded Treatment									Follow-Up
Visit Number	V1	V1a ^a	V2 ^b	V3	V4	V5	V6	V7	V8	V9	ET ^{c,d}	V801 ^{d,e}
Study Week	-6		0	2	4	8	12	16	20	24	any	28 or last dose + 4 weeks
Study Day	-42 to -3		1	15 ± 3	29 ± 4	57 ± 4	85 ± 4	113 ± 4	141 ± 4	169 ± 4	any	197 ± 5 or last dose + 28 ± 5 days
Concomitant medications	X		X	X	X	X	X	X	X	X	X	X
Randomization			X									
Log in IWRS	X		X	X	X	X	X	X	X	X	X	X
Investigational product dispensed			X	X	X	X	X	X	X			
Investigational product returned and compliance assessed				X	X	X	X	X	X	X	X	
Clinical Efficacy												
SLEDAI-2K	X		X	X	X	X	X	X	X	X	X	X
BILAG2004			X	X	X	X	X	X	X	X	X	X
SLEDAI Flare Index (SFI)			X	X	X	X	X	X	X	X	X	X
SLICC			X							X	X	
CLASI			X	X	X	X	X	X	X	X	X	X
28-Tender and Swollen Joint counts			X	X	X	X	X	X	X	X	X	X
Physician's Global Assessment of Disease Activity (VAS)			X	X	X	X	X	X	X	X	X	X
Patient's Global Assessment of Disease Activity ^j	X		X	X	X	X	X	X	X	X	X	X
BPI (Worst Pain) ^j	X		X	X	X	X	X	X	X	X	X	X
BPI (Worst Joint Pain) ^j	X		X	X	X	X	X	X	X	X	X	X
BFI (Worst Fatigue) ^j	X		X	X	X	X	X	X	X	X	X	X
SF-36 ^j			X				X			X	X	X
QIDS-SR ₁₆ ^j	X		X	X	X	X	X	X	X	X	X	X
Laboratory Tests												
TSH	X											

	Screening		Double-Blinded Treatment									Follow-Up
Visit Number	V1	V1a ^a	V2 ^b	V3	V4	V5	V6	V7	V8	V9	ET ^{c,d}	V801 ^{d,e}

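### The Visit 1 scores for SLEDAI-2K and the Patient's Global Assessment could enter the Week 24 models as a second covariate: a small precision gain at almost no cost, once Section 9.4.2 lists the baseline score.

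*Protocol*

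**What the plan says.** In Protocol Appendix 2, the rows for SLEDAI-2K, "Patient's Global Assessment of Disease Activity ^j", worst pain, "BPI (Worst Joint Pain) ^j" and "BFI (Worst Fatigue) ^j" are marked at Visit 1 (screening) and again at Visit 2 (Week 0, before the first dose). Section 4.1 puts 3 to 42 days between the two visits.

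Section 9.2.3 fixes one baseline: "Baseline will be defined as the last available value before the first dose of investigational product for both efficacy and safety analyses". It adds that this will usually be the Visit 2 value.

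Section 9.2.1, like the synopsis, describes continuous efficacy analyses by "mixed-effects models for repeated measures (MMRM) model with treatment, baseline score", then the SLEDAI-2K stratum, anti-dsDNA status, region, visit and treatment-by-visit. No screening score appears.

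Section 9.4.2 deals with change in SLEDAI-2K and change in the Patient's Global Assessment, the two continuous secondary endpoints. These "will be analyzed using MMRM method with treatment, baseline disease activity" (the <10 / ≥10 stratum), anti-dsDNA status, region, visit and treatment-by-visit. That list contains no continuous baseline score.

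**The concern.** A single pre-dose reading is a noisy covariate. The Patient's Global Assessment is one item scored 0 to 4 (Section 8.9.1). The Visit 2 SLEDAI-2K is also the reading on which enrolment criterion [7] is applied, since it must reach 4 "based on clinical symptoms (not including lab values) at randomization", so it will tend to be high by chance and drift back. Visit 1 supplies a second reading of the same patient that was not selected on that threshold. Because it precedes randomisation, adjusting for it introduces no systematic treatment bias, and it may remove outcome variance that one noisy baseline leaves in. What is at stake is the width of the intervals for the two dose comparisons on two secondary endpoints. The data are already being collected.

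**Working it through.** **The plan's own figure.** The only stated power concerns the binary primary endpoint: 100 per arm, 40% against 60%, two-sided 5%. The pooled chi-square without continuity correction gives Φ[(0.20 − 1.96·√(2·0.5·0.5/100)) / √((0.24 + 0.24)/100)] = 81.2%, which agrees with the stated 81%. Nothing below touches it. The protocol gives no standard deviation, target difference or between-visit correlation for the two continuous endpoints, so every correlation here is an assumption.

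**Formulas.** Set the outcome variance to 1. Let a = corr(Visit 1, Visit 2), b = corr(Visit 2, Week 24), c = corr(Visit 1, Week 24).

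- Visit 2 score only: v₁ = 1 − b²
- Both scores: v₂ = 1 − (b² + c² − 2abc)/(1 − a²)
- Cut in residual variance: 1 − v₂/v₁
- Cut in standard error: 1 − √(v₂/v₁)

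**Equal correlation, a = b = c = r (optimistic).** Here v₂ = 1 − 2r²/(1 + r). The last column takes an effect that has 80% power with the Visit 2 score alone.

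| r | v₁ | v₂ | variance cut | SE cut | power, from 80% |
|---|---|---|---|---|---|
| 0.3 | 0.910 | 0.862 | 5.3% | 2.7% | 82.1% |
| 0.4 | 0.840 | 0.771 | 8.2% | 4.2% | 83.2% |
| 0.5 | 0.750 | 0.667 | 11.1% | 5.7% | 84.4% |
| 0.7 | 0.510 | 0.424 | 17.0% | 8.9% | 86.7% |

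This assumes that readings 3 to 42 days apart agree no better than readings 24 weeks or more apart.

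**The two pre-dose readings agree more closely, b = 0.5, v₁ = 0.750.**

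- a = 0.7, c = 0.5: v₂ = 0.706, cut 5.9%
- a = 0.8, c = 0.5: v₂ = 0.722, cut 3.7%
- a = 0.8, c = 0.45: v₂ = 0.743, cut 0.9% (power 80.4%)
- a = 0.8, c = 0.40 (c = ab, so Visit 1 adds nothing): v₂ = 0.750, cut 0%

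**Decay over time plus measurement error.** Let each reading have reliability ρ and let the underlying correlation decay exponentially, with b fixed at 0.5. For a screening gap of d days, with Week 24 at 168 days after Visit 2: q = 0.5/ρ, a = ρ·q^(d/168), c = 0.5·q^(d/168).

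| ρ | cut, d = 14 | cut, d = 42 |
|---|---|---|
| 0.6 | 8.0% | 7.3% |
| 0.7 | 5.3% | 4.3% |
| 0.8 | 3.0% | 2.1% |
| 0.9 | 1.1% | 0.6% |
| 1.0 | 0% | 0% |

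So about 1% to 8% of variance. In standard error this is 1 − √0.99 = 0.5% to 1 − √0.92 = 4.1%. An 8% cut is worth 100/0.92 ≈ 109 patients per arm instead of 100.

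**Averaging is not a substitute.** Replacing Visit 2 by the mean of the two readings gives residual variance 1 − (b + c)²/(2(1 + a)). With a = 0.8, b = 0.5, c = 0.4 this is 0.775 against 0.750, an increase of 3.3%. A separate covariate avoids this risk.

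**Cost.** One extra covariate among about 300 patients inflates variance by about 1/(300 − 8) = 0.3%.

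**Section 9.4.2 as written.** Analysing change with no baseline score leaves variance 2(1 − r) instead of 1 − r², a ratio of 2/(1 + r): 1.54, 1.33 and 1.18 at r = 0.3, 0.5 and 0.7, before whatever the SLEDAI-2K stratum recovers. At each of these values of r that is more than the Visit 1 covariate could save.

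**The case against.** The strongest reply is that nothing here is wrong. A last-value baseline is valid under randomisation, Sections 9.2.1 and 9.2.3 agree on it, and scoring a scale at screening does not commit the sponsor to modelling it. That stands, so the point is put as an efficiency option. The protocol does fix the baseline and the covariate list itself, so proposing one more covariate there is in order.

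Other parts of the reply also stand:

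- A reader might infer that the models for both endpoints already adjust for the Visit 2 score. Section 9.4.2 does not list it, and every saving above is measured against a model that has it.
- A reader might infer that the Visit 1 score is never used. The rule in 9.2.3 makes it the fallback baseline if Visit 2 is missing.
- The 8% to 17% from equal correlations of 0.4 to 0.7 is tempting as a headline. The protocol points to smaller gains: a 7-day recall can overlap when screening is short, and corticosteroids need be stable for only two weeks before randomisation (criterion [28]), so Visit 1 may reflect a different dose. The SLEDAI-2K stratum and anti-dsDNA status already in the model may also absorb part of the signal.
- Regression to the mean from criterion [7] acts equally in all arms, so it is no source of bias.
- Extending the idea to the safety ANCOVAs is not supported. Screening laboratory values are subject to exclusion thresholds and may be repeated (criterion [60]), so there may be no single Visit 1 value.

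None of this shows that the covariate would do harm. A gain of exactly zero needs Visit 1 to carry nothing beyond Visit 2. In the decay model that means a perfectly reliable Visit 2 reading, which is implausible for a one-item, five-point scale.

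**Conclusion.** The point holds as a modest improvement available at almost no cost. It does not show an invalid or biased analysis, and the documents do not support saying that a known amount of precision is lost. With one baseline score in the model, adding the Visit 1 score plausibly cuts residual variance by 1% to 8%, which would move 80% power to somewhere between about 80.4% and 83.2%. The 17% figure needs equal correlation of 0.7 between all three visits, and zero remains possible. All of this rests on assumed correlations. It concerns the two continuous secondary endpoints; pain and fatigue are exploratory. The missing baseline score in 9.4.2 matters more and should be settled first.

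**What to change.** 1. In Section 9.4.2, add the continuous Visit 2 baseline score to the model for both endpoints, so that it agrees with 9.2.1 and the synopsis.
2. In the same edit, add the Visit 1 score of the same scale as a second, separate covariate. Do not average it with Visit 2.
3. Keep change from baseline defined on Visit 2.
4. If the Visit 1 score is missing, set it to the Visit 2 score so that no patient is dropped.
5. Specify all of this before unblinding, since a covariate added later would invite selection.

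The same may be done for the exploratory pain and fatigue scores. The safety ANCOVAs should stay as they are. The cost is a line of model wording and about one degree of freedom per model, with no new data, visits or patients.

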Appendix 3. Clinical Laboratory Tests

Clinical Laboratory Tests^a

Hematology^b	Clinical Chemistry^b
Hemoglobin	Serum Concentrations of:
Hematocrit	Sodium
Erythrocyte count (RBC)	Potassium
Absolute reticulocyte count	Total bilirubin
Mean cell volume (MCV)	Direct bilirubin
Mean cell hemoglobin (MCH)	Alkaline phosphatase (ALP)
Mean cell hemoglobin concentration (MCHC)	Alanine aminotransaminase (ALT)/serum glutamic pyruvic transaminase
Leukocytes (WBC)	Aspartate aminotransferase (AST)/serum glutamic oxaloacetic transaminase
Absolute count of	Blood urea nitrogen (BUN)
Neutrophils, segmented	Creatinine
Neutrophils, juvenile (bands)	Estimated glomerular filtration rate (eGFR) ^c
Lymphocytes	Uric acid
Monocytes	Calcium
Eosinophils	Glucose ^d
Basophils	Albumin
Platelets	Creatine phosphokinase (CPK)
Cell morphology	Total protein
Differential and blood smear ^e	
Iron studies (iron, TIBC, and ferritin)	
Lymphocyte subsets (T, B, NK, and T-cell subsets)	Lipid Profile^{d,f}
	Total cholesterol
	High-density lipoprotein cholesterol (HDL-C)
	Low-density lipoprotein cholesterol (LDL-C)
	Triglycerides
Urinalysis^b	
Color	
Specific gravity	
pH	
Protein	Other Tests
Glucose	Serum pregnancy test (females only) ^g
Ketones	Urine pregnancy test (females only) ^g
Blood	Follicle-stimulating hormone (FSH) (females only) ^h
Bilirubin	Hepatitis B surface antigen (HBsAg)
Urobilinogen	Hepatitis B surface antibody (HBsAb)
Leukocyte esterase	Hepatitis B core antibody (HBcAb)
Nitrite	Hepatitis C antibody ⁱ
Urine creatinine	HBV DNA ^k
Microscopic examination of sediment ^j	Human immunodeficiency virus (HIV) serology
	PPD or QuantiFERON®-TB Gold, or T-SPOT®.TB ^l
	Thyroid-stimulating hormone (TSH)
Anti-nuclear antibody (ANA)	High-sensitivity C-reactive protein (hsCRP)
Anti-double-stranded DNA (anti-dsDNA) antibody	Stored serum, plasma, urine, mRNA ^m , and DNA samples for exploratory biomarker analyses
Autoantibodies (anti-RNP, anti-Sm, anti-SSA/Ro, anti-SSB/La)	Serum immunoglobulins (IgG, IgA, IgM)
Antiphospholipid antibodies	Baricitinib plasma concentration (PK sample)
Complement C3 and C4	

Abbreviations: HBV DNA = hepatitis B virus deoxyribonucleic acid; mRNA = messenger ribonucleic acid; PK = pharmacokinetics; PPD = purified protein derivative; RBC = red blood cells; TIBC = total iron binding capacity; WBC = white blood cells.

^a All labs will be assayed/calculated by a Lilly-designated laboratory unless otherwise noted.

- b Unscheduled blood chemistry (including CPK), hematology, and urinalysis panels may be performed at the discretion of the investigator. If tests are done to evaluate laboratory results to resume investigational product, samples must be assayed centrally.
- c eGFR for serum creatinine will be calculated by the central laboratory using the Modification of Diet in Renal Disease (MDRD) isotope dilution mass spectrometry traceable method.
- d Fasting laboratory values for glucose and lipids will be required at baseline, Week 12, and Week 24. If a patient attends these visits in a nonfasting state, this will not be considered a protocol violation. These tests may be performed nonfasting at all other visits.
- e Differential and blood smear may be performed if necessary.
- f Lipid panel consists of direct HDL-C, triglycerides, cholesterol, and LDL-C (calculation from Friedewald et al. 1972).
- g For all women of childbearing potential, a serum pregnancy test (central laboratory) will be performed at Visit 1, and both urine (local laboratory) and serum pregnancy (central laboratory) tests will be performed at Visit 2 to determine study eligibility. Urine pregnancy tests (local laboratory) will also be performed at each subsequent study visit per the Schedule of Activities.
- h To confirm postmenopausal status for women ≥ 40 and < 60 years of age, an FSH test will be performed. Nonchildbearing potential is defined as an FSH ≥ 40 mIU/mL and a cessation of menses for at least 12 months.
- i A positive hepatitis C antibody result will be confirmed with a positive hepatitis C virus result.
- j Microscopic examination of sediment will be performed if abnormalities are noted on the routine urinalysis.
- k HBV DNA testing will be performed in patients who tested positive for HBcAb at screening. Patients who are HBcAb positive and HBV DNA negative at Visit 1 will require HBV DNA monitoring every 3 months, at an early termination (ET) visit, and at Visit 801, regardless of their HBsAb status. If the HBV DNA result is above the lower limit of quantification (LLOQ), refer to Section 7.1.2 and Section 8.4.4. For study sites in Japan (or elsewhere if required), if a patient is HBcAb positive and/or HBsAb positive and negative for HBV DNA at Visit 1, HBV DNA needs to be checked at least monthly and at the patient's last visit.
- l PPD, QuantiFERON®-TB Gold, and T-SPOT®.TB tests may be performed locally. Test will be required at Visit 1 only to determine eligibility of patient for the study. In countries where the QuantiFERON-TB Gold or T-SPOT.TB test is available and, in the judgment of the investigator, medically preferred as an alternative to the PPD test for the evaluation of mycobacterium tuberculosis (MTB) infection, either may be used instead of the PPD test (positive tests excluded).
- m Interferon (IFN) signature will be assayed from stored mRNA sample.

